## **ABSTRACT**

### **• PROTOCOL TITTLE**

Prospective observational study on the analgesic effectiveness of blocking the shoulder's anterior capsule and the suprascapular nerve by the anterior approach versus blocking of the suprascapular and axillary nerves by the posterior approach in shoulder arthroscopy.

### **• PROTOCOL CODE**

SHAC

### **• STUDY DESIGN**

An observational study of paired cohorts, not randomized, is designed in two hospitals in northern Spain in the period between october 2023 and september 2024.

### **• MAIN AND SECONDARY OBJECTIVES**

#### **Main:**

The measurement of pain intensity according to the numerical rating scale (NRS) at different times: preoperative and at the 1st, 2nd, 12th and 24th postoperative hours.

#### **Secondary:**

Postoperative opioid consumption and comparison of total cumulative consumption between the two groups.

It will also evaluated the degree of sensory and motor block, the easy of performance of the anesthetic technique, the degree of patient satisfaction and the record of short-term complications (first 24 hours post-intervention): hematoma, pruritus, nausea and/or vomiting.

### **• Study population and total number of subjects.**

All patients consecutively scheduled for arthroscopic unilateral rotator cuff repair of the shoulder, who meet the inclusion criteria will be recruited for the study.

## BACKGROUND AND JUSTIFICATION OF THE PROJECT

Arthroscopic shoulder surgery is related to a high incidence of postoperative pain, being rated as intense by 45% of patients in the immediate postoperative period (1). The management of these patients can be complex due to the high incidence of preoperative pain and its variability during the postoperative period, which is higher in patients undergoing rotator cuff repair surgery (2).

It is crucial to ensure adequate postoperative pain control in this type of intervention, especially in the context of major outpatient surgery. Adequate postoperative pain control can have several benefits, such as reducing hospital stay (3), accelerating postoperative rehabilitation (4), and improving long-term outcomes (5).

The PROSPECT guideline for rotator cuff repair surgery recommends associating a regional analgesic technique with a multimodal pharmacological approach to pain. (6).

Traditionally, the interscalene block has been considered the gold-standard for analgesia in shoulder surgery; However, its possible serious complications limit its use. Currently, most anesthesiologists choose to perform more distal peripheral nerve blocks of the brachial plexus (upper trunk block, supraclavicular block, infraclavicular block at the costoclavicular level, axillary nerve block...) which, although highly effective, continue to cause impairment. prolonged motor activity and are not free of complications (phrenic paralysis, transient nerve injuries, inadvertent vascular punctures...) (7).

Shoulder anterior capsular block (SHAC) has recently been described. It is a fascial block of the anterior capsule of the shoulder that aims to avoid motor impairment while maintaining optimal analgesic efficacy (8)(9). However, so far only anatomical and descriptive studies of small case series have been published. Therefore, this research work, with the objective of comparing the postoperative analgesic effectiveness of two regional analgesic techniques: the SHAC block associated with the suprascapular nerve block performed anteriorly vs. suprascapular and axillary nerve blocks performed posteriorly in operated patients. of the shoulder via arthroscopic procedures that cause intense postoperative pain.

## **STUDY HYPOTHESES**

Two analgesic strategies included within the usual clinical practice will be compared for postoperative pain control after shoulder arthroscopy. With this study we want to compare the ultrasound-guided block of the suprascapular nerves and the shoulder joint capsule via the anterior route versus the ultrasound-guided block of the suprascapular and axillary nerves via the posterior route.

### **GOALS:**

- **Main objective**

The measurement of pain intensity according to the NRS at different times: preoperative and at the 1st, 2nd, 12th and 24th postoperative hours.

- **Secondary objectives**

Postoperative opioid consumption and comparison of total cumulative consumption between the two groups.

It will also evaluated the degree of sensory and motor block, the easy of performance of the anesthetic technique, the degree of patient satisfaction and the record of short-term complications (first 24 hours post-intervention): hematoma, pruritus, nausea and/or vomiting.

## **STUDY TYPE**

An observational study of paired cohorts, not randomized, is designed in two hospitals in northern Spain in the period between october 2023 and september 2024.

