## PROTOCOL

All patients will be trained preoperatively in pain assessment using a Numerical Rating Scale (NRS) from 0 (absence of pain) to 10 (maximum pain endured). All patients will receive the same anesthesia and analgesia protocol; fentanyl, propofol and rocuronium prior to intubation.

Anesthetic maintenance with 1 MAC of sevoflurane and boluses of muscle relaxant and fentanyl if there is an increase >20% in blood pressure or above baseline heart rate. The anesthetic protocol will include analgesia with 1 g of paracetamol and 50 mg of dexketoprofen every 8 hours and a bolus of 0.1 mg/kg of intravenous dexamethasone. When the patient reports an NRS > 3 and functional impact, intravenous morphine will be administered at a dose of 0.04 mg/kg every 10 minutes until NRS < 3 in the PACU and tramadol 1 mg/kg in the ward. The nursing staff and the anesthesiologist in charge of the PACU will be blind to the block received by the patient in each study group.

Before general anesthesia, patients will be assigned to one of the study groups depending on the anesthesiologist responsible for performing the blocks.

**SHAC + SSN Group (anterior approach):** with the patient in the supine position and the arm placed in abduction and slight external rotation the ultrasound probe will be positioned in the transverse axis between the coracoid process and the humeral head. After identifying the tendon of the subscapularis muscle, a puncture will be performed in a lateral to medial plane and the local anesthetic will be deposited at two levels; one deep to the subscapularis tendon at the pericapsular level of the glenohumeral joint (5 ml of ropivacaine 0.2%), and another in withdrawal at about the level of the fascia that separates the subscapularis and deltoid muscles at a more superficial level (10 ml of 0.2% ropivacaine). Subsequently, the ultrasound probe will be positioned in the transverse axis at level with the neck to locate the suprascapular nerve through an anterior approach as it ran beneath the omohyoid muscle. After hydrodissecting the correct plane with saline solution 5 ml of 0.2% ropivacaine will be administered, depositing the local anesthetic under the lower belly of the omohyoid muscle.

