## **RECRUITMENT AND RECRUITMENT OF PARTICIPANTS**

The anesthesiologist responsible for the operating room performed both the block of the anterior capsule of the shoulder and the suprascapular nerve via the anterior route and the blocks of the suprascapular and axillary nerves via the posterior route until the number of patients established in each of the groups is reached.

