## **JUSTIFICATION OF SAMPLE SIZE**

Because no work of this nature has been carried out previously, a sample size calculation will be not performed and all patients who underwent surgery in the 12 months that the study data collection will last were consecutively included in the study.

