## **STATISTICAL ANALYSIS PLAN**

Continuous quantitative variables will be expressed as mean and standard deviation and the results will be contrasted using the Student's T test if normality criteria will be met, failing which they will be expressed as median and range and contrasted using the Mann Whitney's U. The qualitative variables will be expressed in absolute numbers and relative frequencies and the results of both groups will be contrasted using the Chi square. In addition, Fisher's test will be applied when necessary. Normality tests will be conducted for all continuous quantitative variables. The Kruskal-Wallis technique will be also employed with post-hoc application of the Bonferroni test for the analyses. The data will be processed using SPSS software version 19.0 (IBM Corporation, Armonk, NY, USA), assuming a p-value below 0.05 as significant.

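### The study is labelled as paired cohorts, but no pairs are formed, and the main comparison of non-randomised groups is planned without any adjustment

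*Combined protocol and SAP*

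**What the plan says.** The design label appears twice: in the abstract under Study Design ("An observational study of paired cohorts, not randomized") and in the body under Study Type ("An observational study of paired cohorts, not randomized, is designed in two hospitals").

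The sections that describe how patients enter the study and reach a group are these:

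- Abstract, Study population: "All patients consecutively scheduled for arthroscopic unilateral rotator cuff repair of the shoulder, who meet the inclusion criteria will be recruited".
- Protocol section: "patients will be assigned to one of the study groups depending on the anesthesiologist responsible for performing the blocks".
- Recruitment section: blocks are performed "until the number of patients established in each of the groups is reached". That number is not given anywhere.
- Justification of Sample Size: no calculation is made, and "all patients who underwent surgery in the 12 months that the study data collection will last were consecutively included in the study".

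The Statistical Analysis Plan names Student's t test with Mann-Whitney U as the non-normal alternative, and Kruskal-Wallis with Bonferroni. For qualitative variables "the results of both groups will be contrasted using the Chi square", with Fisher's test where needed. It names no paired test, no regression and no covariate. Variables Evaluated lists preoperative NRS as one of the measured time points.

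**The concern.** In a non-randomised comparison, readers take *paired* to mean that patients in one group were matched to patients in the other, so that the groups are alike on the matching variables. Here it is the only word in the design or analysis description that suggests comparability was built in.

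If no matching takes place, the difference in NRS between the groups carries any difference in who was treated, by whom and where. Group depends on the anesthesiologist and there are two hospitals, so differences in preoperative pain, case mix and local practice may all line up with the block received. The Background section itself says that preoperative pain is common in these patients. Preoperative NRS is collected, yet no planned analysis uses it to adjust the postoperative comparison. A reader who trusts the label would draw a firmer conclusion than the analysis can support.

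**Working it through.** The plan states no sample size, power or effect size, so there is no figure of its own to reproduce. The check is a reading of the text, followed by the arithmetic for the conditional case.

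**Step 1. Is there a pairing step?** A matched cohort needs matching variables, a ratio, a rule for choosing matches and a rule for patients without one.

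| Element | What the document gives |
|---|---|
| Matching variables | none |
| Ratio, caliper or algorithm | none |
| Patients without a match | not addressed |
| Entry to study | consecutive, all eligible |
| Entry to group | by anesthesiologist |
| End of group filling | an unstated number per group |

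None of these steps creates a pair. Consecutive inclusion with grouping by operator describes two unmatched cohorts.

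**Step 2. Do the tests use pairs or covariates?** Mann-Whitney U, Chi-square, Fisher and Kruskal-Wallis are all independent-samples methods. The form of Student's t test is not stated, but its fallback is Mann-Whitney rather than the signed-rank test, which implies the independent form. There is no paired t, signed-rank, McNemar, conditional or mixed model, and no covariate adjustment.

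**Step 3. If the cohorts are unmatched (the likelier reading).** The tests fit the independence structure the word *paired* would otherwise contradict, so the label creates no standard-error fault. What remains is confounding. If the groups differ by *d* in mean preoperative NRS, and postoperative NRS rises by *b* per point of preoperative NRS, the unadjusted difference is shifted by *b* × *d*. The documents give neither value, so this bias cannot be sized. The same reasoning applies to hospital.

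**Step 4. If individual 1:1 pairs did exist.** Let the within-pair correlation be ρ, with equal variances σ² and n pairs. The document gives no ρ; the values below are assumptions.

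- True variance of the mean difference: 2σ²(1 − ρ)/n. The independent-samples test uses 2σ²/n.
- Ratio of standard errors, unpaired to paired: 1/√(1 − ρ).
- Actual two-sided type I error at nominal 0.05: 2 × [1 − Φ(1.96/√(1 − ρ))]. The plan does not state sidedness; two-sided is assumed.

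| ρ (assumed) | SE ratio | Actual type I error |
|---|---|---|
| −0.2 | 0.91 | 0.074 |
| 0 | 1.00 | 0.050 |
| 0.1 | 1.05 | 0.039 |
| 0.2 | 1/√0.8 = 1.12 | 0.028 |
| 0.3 | 1/√0.7 = 1.20 | 0.019 |
| 0.5 | 1/√0.5 = 1.41 | 0.006 |

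A simulation of 20,000 runs with 30 pairs, ρ = 0.3 and a true difference of 0.5 SD (all assumed) agrees. Type I error is 0.020 for the unpaired t test and 0.050 for the paired t test; power is 0.47 against 0.60. With positive ρ, ignoring pairs loses power and makes the test conservative.

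**The case against.** The strongest reply is that *paired* is loose wording. The document also calls the study cross-sectional (Risks) and an anonymous survey (Ethical-Legal Aspects), so its design labels are unreliable in general. On this view one adjective is wrong, the tests are acceptable, and the lack of adjustment would be the same had the word never been used. Much of this stands: unmatched cohorts are the likelier reading. It does not remove the point, because the label appears in both the abstract and the body, and deleting it leaves a non-randomised comparison with no adjustment.

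A second reply is that *paired* may mean frequency matching or groups of equal size, in which case unpaired tests are not plainly wrong. The document neither confirms nor excludes this. For that reason a reader should not infer that the design and the tests cannot both be right.

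A third reply is that the plan does limit some differences: it restricts eligibility, uses one anesthesia and analgesia protocol for all, and blinds the PACU nurses and anesthesiologist. That is fair, and it would be too strong to say that nothing guards against bias. None of these measures, however, balances preoperative pain, hospital or operator between the groups.

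**Conclusion.** The point holds as one of design description and confounding. The plan declares a paired design that it does not deliver, and its main comparison of non-randomised groups across two hospitals is unadjusted although preoperative NRS is collected. The size of the resulting bias cannot be calculated from the documents.

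A reader might go further and infer that the planned standard errors are wrong by 12% to 41%. The documents do not support that. Those figures need individual 1:1 pairs, of which there is no trace, and an assumed ρ of 0.2 to 0.5. At ρ = 0 there is no error. With positive ρ the error is conservative, so a significant result would not be put in doubt by it; only a negative ρ would reverse the direction.

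**What to change.** 1. Delete *paired* in the abstract (Study Design) and in Study Type, and describe the study as unmatched, non-randomised cohorts.
2. Make the main comparison of postoperative NRS a regression, or a repeated-measures model over hours 1, 2, 12 and 24, adjusted for preoperative NRS and hospital. Add age and ASA class if they are recorded. Preoperative NRS then serves as a covariate rather than as one of the outcomes.
3. Keep simple tests for sparse outcomes such as hematoma and pruritus, where a model with several covariates may not be estimable.
4. State whether each anesthesiologist gives one technique or both; the Protocol and Recruitment sections leave this unclear. If each gives only one, state as a limitation that an anesthesiologist effect cannot be separated from the effect of the block.
5. Only if individual pairs are truly formed, name the matching variables, the ratio and the handling of unmatched patients. Then use paired t, Wilcoxon signed-rank and McNemar tests, or a model with a pair term.

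The cost is a wording change in two places, a new paragraph in the analysis plan and some extra analysis work. Preoperative NRS is already collected and hospital is known for every patient. Age and ASA class bear on eligibility but are not in the list under Variables Evaluated, so their recording needs to be confirmed.

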## PROTOCOL

All patients will be trained preoperatively in pain assessment using a Numerical Rating Scale (NRS) from 0 (absence of pain) to 10 (maximum pain endured). All patients will receive the same anesthesia and analgesia protocol; fentanyl, propofol and rocuronium prior to intubation.

Anesthetic maintenance with 1 MAC of sevoflurane and boluses of muscle relaxant and fentanyl if there is an increase >20% in blood pressure or above baseline heart rate. The anesthetic protocol will include analgesia with 1 g of paracetamol and 50 mg of dexketoprofen every 8 hours and a bolus of 0.1 mg/kg of intravenous dexamethasone. When the patient reports an NRS > 3 and functional impact, intravenous morphine will be administered at a dose of 0.04 mg/kg every 10 minutes until NRS < 3 in the PACU and tramadol 1 mg/kg in the ward. The nursing staff and the anesthesiologist in charge of the PACU will be blind to the block received by the patient in each study group.

Before general anesthesia, patients will be assigned to one of the study groups depending on the anesthesiologist responsible for performing the blocks.

**SHAC + SSN Group (anterior approach):** with the patient in the supine position and the arm placed in abduction and slight external rotation the ultrasound probe will be positioned in the transverse axis between the coracoid process and the humeral head. After identifying the tendon of the subscapularis muscle, a puncture will be performed in a lateral to medial plane and the local anesthetic will be deposited at two levels; one deep to the subscapularis tendon at the pericapsular level of the glenohumeral joint (5 ml of ropivacaine 0.2%), and another in withdrawal at about the level of the fascia that separates the subscapularis and deltoid muscles at a more superficial level (10 ml of 0.2% ropivacaine). Subsequently, the ultrasound probe will be positioned in the transverse axis at level with the neck to locate the suprascapular nerve through an anterior approach as it ran beneath the omohyoid muscle. After hydrodissecting the correct plane with saline solution 5 ml of 0.2% ropivacaine will be administered, depositing the local anesthetic under the lower belly of the omohyoid muscle.

**SSN + AN group (posterior approach):** with the patient in a sitting position and the arm placed in a neutral position, with slight internal rotation supported on the abdomen, the ultrasound probe will be positioned in the supraspinous fossa and a first puncture of the suprascapular nerve will be performed posteriorly, level with the supraspinous fossa. Next, the probe will be positioned at the level of Velpeau's quadrilateral and a second puncture of the axillary nerve will be performed, taking the posterior humeral circumflex artery as a sonoanatomical reference in the plane of intersection formed by the deltoid, triceps brachii, and teres minor muscles. After locating the planes by hydrodissection with saline solution 10 ml of 0.2% ropivacaine will be administered to each of the nerves.

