## **VARIABLES EVALUATED**

The main variable will be the measurement of pain intensity according to the NRS at different times: preoperative and at the 1st, 2nd, 12th and 24th postoperative hours. As secondary variables, postoperative opioid requirements will be assessed in the form of intravenous morphine, measured in mg (only during the 2 hours of the patient's stay in the Postanesthesia Care Unit), and tramadol (mg) up to 24 hours postoperatively.

The degree of sensory block will be also assessed by a cold sensitivity test with a cotton swab dipped in cold water applied to the skin of the upper third of the arm, which will be graded with a sensitive scale going from 0 to 2 (2 being normal sensitivity to cold, 1 hypoesthesia and 0 anesthesia). The degree of motor block upon arrival at the PACU will be assessed by the movement of the arm using a simple numerical scale (0 = cannot raise the extended arm  $> 45^\circ$  and 1 = can raise the extended arm  $> 45^\circ$ ), the ease of performance of the corresponding anesthetic technique by the anesthesiologist using a simple verbal scale (easy/medium difficulty/difficult), the appearance of adverse effects (postoperative nausea and/or vomiting, hematoma, pruritus, urinary retention), the degree of patient satisfaction (very satisfied, satisfied or dissatisfied) and the notification of complications related to the anesthetic techniques performed.

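### The single motor-block score on PACU arrival cannot separate nerve block from residual relaxant, opioid or sedation, and the relaxant trigger can be read as depending on how well the block works

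*Combined protocol and SAP*

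**What the plan says.** All references are to the combined protocol and SAP.

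- **PROTOCOL, induction:** every patient receives "fentanyl, propofol and rocuronium prior to intubation". No rocuronium dose is given.
- **PROTOCOL, maintenance:** sevoflurane plus "boluses of muscle relaxant and fentanyl if there is an increase >20% in blood pressure or above baseline heart rate". A single conditional clause follows the two drugs, and no other trigger for the relaxant appears.
- **PROTOCOL, allocation and blinding:** blocks precede general anaesthesia, and "patients will be assigned to one of the study groups depending on the anesthesiologist responsible for performing the blocks". The PACU nurses and the PACU anaesthesiologist "will be blind to the block received by the patient in each study group". Nothing is said about blinding of intraoperative dosing.
- **VARIABLES EVALUATED:** "The degree of motor block upon arrival at the PACU will be assessed by the movement of the arm using a simple numerical scale", where 0 means the extended arm cannot be raised above 45° and 1 means it can. The text does not say which arm. This is the only motor assessment described. Of the opioids, only postoperative morphine and tramadol are listed for recording.
- **GOALS:** among the secondary objectives, "It will also evaluated the degree of sensory and motor block".
- **BACKGROUND:** the SHAC block "aims to avoid motor impairment while maintaining optimal analgesic efficacy".
- **STATISTICAL ANALYSIS PLAN:** for qualitative variables, "the results of both groups will be contrasted using the Chi square", with Fisher's test where needed. No adjustment is described.

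The document mentions no check of recovery before the motor score, no comparison limb, and no recording of intraoperative relaxant or fentanyl doses.

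**The concern.** A score of 0 on PACU arrival can arise from the block, or from relaxant, opioid or sedation that has not worn off. The plan records nothing that would tell these apart.

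That would be simple noise if the other causes were unrelated to group. They may not be. The blocks are in place before surgery, so they can change the haemodynamic response to it. If that response triggers relaxant as well as fentanyl, a co-treatment that depends on the study block also acts on the endpoint. A block giving poorer intraoperative analgesia could then be credited with more motor block. PACU blinding does not help, because this is a drug effect on the patient and not an observer effect.

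Motor sparing is the stated purpose of the new technique, so this score bears directly on one of the claims that readers will look for.

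**Working it through.** **Reproducing the plan's figure.** There is none. The document states no motor-block rate, sample size or power. The first step is therefore a reading check, and the second is an illustration on assumed inputs.

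**Step 1. Two readings of the trigger sentence.**
- *Reading A:* the clause governs both drugs. A weaker block means more haemodynamic responses, hence more relaxant and fentanyl, and possibly a score of 0.
- *Reading B:* the clause governs fentanyl only. The path from weaker block to more relaxant is gone. Relaxant acts mostly alike in both groups. Fentanyl can still follow block quality, and dosing habits can still differ by group because allocation follows the anaesthesiologist.

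Under both readings the motor score comes soon after general anaesthesia with no means of isolating the block.

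**Step 2. Size under reading A.** All inputs are assumptions:
- p = true motor-block rate
- q = share of patients given relaxant boluses
- f = chance that residual relaxant alone stops a bolused patient raising the arm

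Observed rate of score 0 = p + (1 − p) × q × f. Residual effect from the induction dose is left out.

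*Equal true rates, p = 20% in both groups; q = 80% (weaker block) and 20%:*

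| f | Weaker block | Stronger block | False difference |
|---|---|---|---|
| 0 | 20.0% | 20.0% | 0 |
| 0.05 | 0.20 + 0.80×0.80×0.05 = 23.2% | 0.20 + 0.80×0.20×0.05 = 20.8% | +2.4 points |
| 0.10 | 26.4% | 21.6% | +4.8 points |
| 0.30 | 39.2% | 24.8% | +14.4 points |

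With q = 50% and 20%, the shift is +2.4 points at f = 0.10 (24.0% vs 21.6%) and +7.2 at f = 0.30 (32.0% vs 24.8%).

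*Chance of a false significant result.* With an assumed 50 per group, a two-sided 0.05 test and the normal approximation, the chance of significance in the direction of the bias at q = 80%/20% is about 8% at f = 0.10 and 34% at f = 0.30. Without bias it would be 2.5% in that direction.

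*A true difference, weaker block 20% and stronger block 30% (−10 points), q = 80%/20%:*
- f = 0.10: 26.4% vs 0.30 + 0.70×0.20×0.10 = 31.4%, so −5.0 points
- f = 0.30: 39.2% vs 34.2%, so +5.0 points, a reversal

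**Step 3. Size when exposure is equal in the groups (approximately reading B).** With q = 50% in both groups and f = 0.30, the same −10 points becomes 32.0% vs 40.5% = −8.5. Equal true rates stay equal. More generally, if a share r of patients without true block fail in each group, the difference shrinks by the factor (1 − r): a true 20 points becomes 20×0.95 = 19 at r = 5% and 20×0.80 = 16 at r = 20%.

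**Step 4. What a large bias would require.** Since r = q × f, a 20-point gap in r between groups at q = 80%/20% needs f = 0.20/0.60 = 0.33. A 10-point gap needs f = 0.10/0.60 = 0.17, or 0.10/0.30 = 0.33 at q = 50%/20%.

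**The case against.** The strongest case against has four parts.

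1. **The trigger may not be shared.** The relaxant link rests on one ambiguous sentence. This stands: a reader might infer that the protocol definitely ties relaxant to haemodynamic signs, but the wording does not settle it.
2. **Silence is not absence.** The anaesthetic description is a short outline, common to both groups, that omits routine detail, and STUDY HYPOTHESES places both techniques within usual practice. Not mentioning monitoring or reversal does not show that neither is done, or that any patient arrives weak. This stands too: a reader might infer that residual paralysis will occur, and the documents give no evidence of it.
3. **The outcome is secondary and nothing is powered on it.** This is correct. The mechanism does not directly touch the NRS scores.
4. **A control arm is an imperfect remedy.** It cannot remove pain or surgical limitation in the operated shoulder. A mild relaxant effect added to a partial block could still let the control arm pass and the operated arm fail. Repeating the test later only in patients who fail with both arms would make the timing of the score depend on group. These limits shape the fix but do not remove the case for it.

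What the objection does not answer is that, as planned, the data could not show whether the bias is absent, small or large.

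**Conclusion.** The point holds as a measurement weakness in a secondary outcome, worth correcting because the correction is nearly free. The motor score cannot isolate the block under either reading of the trigger. Bias that favours one technique through the relaxant follows only if the trigger covers both drugs, bolus use differs between groups, and some bolused patients are still weak on arrival.

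At residual-weakness rates of 5% to 10% among bolused patients, the false difference is about 2 to 5 points even with bolus shares as far apart as 80% and 20%. Double-digit differences or a reversal need rates well above that. Every one of these rates is assumed.

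It would be tempting to conclude that the motor-block comparison will be biased against the weaker block, or that the study's main result is unsafe. The documents support neither conclusion.

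**What to change.** 1. In VARIABLES EVALUATED, name the operated arm, and score the same raise above 45° in the non-operated arm at the same moment on PACU arrival, in every patient.
2. Count block-related motor impairment only when the non-operated arm passes and the operated arm fails. Report patients in whom both arms fail as not evaluable, with counts by group.
3. If a 1-hour motor score is wanted, take it in all patients and report it as its own time point. Do not use it to replace arrival scores in selected patients.
4. Record total intraoperative relaxant and fentanyl doses and report them by group.
5. In PROTOCOL, state which drug or drugs the haemodynamic trigger governs, so that this passage can be reconciled with the motor score. This asks for clarification only; no change to anaesthetic care is proposed.

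**Cost:** a few seconds per patient, extra data fields, and a few scores lost as not evaluable. Limitation from pain or surgery in the operated shoulder remains and should be acknowledged when the result is reported.
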